4.0 Research participants

4.1 Characteristics of research participants

The study will enroll eligible, consenting women aged 18 and older. Eligible women will be informed about the study and invited to participate. The legal age of consent in El Salvador, Colombia and China is 18 years of age.

4.2 Inclusion and exclusion criteria

Women who present to the health facility for biopsy results and meet the study criteria will be invited to participate in the study. We will collect delinked, anonymous, pooled data (e.g., age, geographic area of residence, and diagnosis) on all women, including those who decline to participate, to characterize them and assess whether our study population is representative of the general population.

Criteria for Inclusion

- Women aged 18 and older
- Biopsy results of CIN2, CIN2-3, CIN3, or high-grade CIN not otherwise specified (quality assurance will be performed by an expert gynecologic pathologist)
- Willing and able to provide informed consent
- Willing and able to provide permanent or reliable address

Criteria for Exclusion

- Pregnant or plans to become pregnant during study
- History of total hysterectomy (verified by medical record or pelvic evaluation)
- Previous surgery destructive to the cervix within the last 5 years
- Patient not eligible for cryotherapy (1) lesion extends to over 75% of the cervix, 2) lesion is too large to be covered by the cryotherapy probe, 3) lesion extends into the endocervical canal, 4) the cervix is distorted or has severe atrophy; 5) the cervix is not visible, 6) the squamo-columnar junction is not completely visible, 7) the cervix is hard to reach, and/or 8) suspicion of cancer)
- Cervix shape disfigured or hard to reach

4.3 Withdrawal from the study

Women who sign the informed consent to participate in the study have the right to withdraw their consent at any time during the study. Physicians performing the ablation procedures have the right to remove participants from the study if, upon pelvic examination, the condition of the cervix is not conducive to continuing the procedure.

5.0 Study procedures

5.1 Initial Exam

After a woman consents to participate in the research study and meets other eligibility criteria including testing negative on a pregnancy test, she will answer a short survey with demographic and life history information relevant to the study (i.e., age, location of residence relative to clinic, smoking and sexual history, parity and history of vaginal surgeries). Next, the provider will initiate the ablation procedure by performing a pelvic exam. If the provider determines during this exam that the condition of the cervix is not conducive to an ablation procedure for anatomical reasons, the participant will be removed from the study.

5.2 Study procedures for cervical ablations

For the traditional cryotherapy arm, providers will use a MedGyn cryotherapy unit with a 19 or 25 mm conical tip supplied with a refillable tank of medical grade CO₂. For the experimental CryoPen[®] arm, providers will use LMIC-adapted CryoPen[®] prototype with a 19 mm conical tip. For the thermoablator arm, providers will use a handheld WISAP thermoablator (model C3) with a 20 mm conical tip.

Anesthesia is not required for cervical ablation procedures and none will be provided routinely in this research study. Analgesics may be prescribed for discomfort after the procedure. Study coordinators will verbally ask study participants to assess their pain

using the Wong Baker Faces Scale (Figure 2),¹³ a well-validated and widely used self-assessment tool. This scale was originally developed for use with children but is now available in many languages, including Spanish and Mandarin Chinese, and is used to improve communication between patients and providers. It utilizes five simple drawings of faces depicting different levels of pain, each shown above a number from 0 (no pain) to 10 (worst possible pain). Patients can use the expressions on the faces to rate their own experience according to the corresponding number. Pain will be assessed at 4 points: before speculum insertion (baseline), after speculum insertion but before treatment, during treatment, and after speculum removal.

Wong-Baker FACES™ Pain Rating Scale

Figure 2. FACES and numeric pain rating scale

Cervical photographs will be taken immediately pre- and post-procedure for participants who have consented to photographs. Photographs will provide additional documentation of the cervix anatomy to corroborate the clinical evaluation whether the anatomy of the cervix could have interfered with a good contact by the treatment probe at cervix positions 3, 6, 9 or 12 (as on a clock face).

Each study procedure is estimated to take approximately 10-15 minutes. The remainder of the time will be spent preparing the participant and taking cervical photographs. The six-week and 12-month follow-up visits (described in section 3.1) are expected to take about 15 minutes. All women will undergo liquid-based cytology, VIA, and HPV testing. Women suspected of having invasive cancer at the follow-up visit will be referred for appropriate management.

5.2.1 CO₂-based cryotherapy procedure

- Study physicians will use MedGyn cryotherapy units supplied with a refillable tank of medical grade CO₂ and a 19 or 25 mm conical tip.
- A pressure gauge attached to the compressed gas tank shows the cylinder gas pressure. If there is adequate gas pressure in the cylinder (40-74 kg/cm²), the indicator moves to the green zone in the gauge when the cryogun releases the gas. The pressure must be in the green zone or there will be insufficient freezing for cryotherapy.
- The cervix is exposed after a speculum is placed to separate the vaginal walls.
- The cryotherapy probe tip is applied with the center of the tip on the external os. The probe should adequately cover the lesion and should not come in contact with any part of the vagina during the procedure.
- The gas trigger in the cryogun is squeezed to administer the freeze. An ice ball will form on the tip of the cryoprobe and on the cervix throughout the freeze.

- A double freeze is applied.
- The cryoprobe is removed by gently rotating on the cervix once complete thawing has occurred and the ice ball has cleared.
- The cryoprobe and tip must be disinfected using a high-level disinfectant.

5.2.2 CryoPen® procedure

- Study physicians will use the LMIC-adapted CryoPen® with a 19 mm conical tip.
- The CryoPen unit is plugged into an electrical outlet. The well is filled with ethanol. The unit is ready for use when the light on the temperature indicator turns green.
- The tip is placed on the applicator and twisted in place.
- The core is removed from the unit and the well is closed to prevent the well from freezing.
- The core is inserted into the applicator and pulled against the core handle to hold the device together.
- The core and the applicator are inserted together into the vagina and the tip is placed on the cervix.
- When the procedure is completed the core is removed first. Once complete thawing has occurred, the applicator is then removed by gently rotating the tip.
- If the entire SCJ is not frozen, providers may repeat the application once more until the entire SCJ is ablated.
- The core is then returned to the CryoPen® unit. Frost must be wiped from the core with a towel before the core is inserted into the well.
- The applicator must be discarded and the core tip must be disinfected using a high-level disinfectant.

5.2.3 Thermoablator

- Study physicians will use a handheld thermoablator with a 20 mm conical tip, manufactured and sold by WISAP Medical Technology (Germany).
- The probe and protector slider are connected to the unit and the unit is plugged into an electrical outlet.
- The unit is turned on when the power button is pressed to the "on" position. The switch illuminates green and starts blinking as the therapy probe tip begins to heat up.
- Unit is ready for use when the green temperature indicator light stops blinking.
- The physician slides the protector forward to cover the probe tip.
- When the probe makes contact with the cervix, the protector is moved back.
- The probe tip is applied to the cervix for 40 seconds.
- The protector is slid back to cover the tip.
- The probe is removed and the physician visually evaluates the cervix to ensure the entire SCJ has been ablated.
- In some cases, providers may continue with additional 20 second applications until the entire SCJ is ablated.
- When the procedure is completed the unit is turned off and the probe and protector are removed for disinfection with a high-level disinfectant.

5.3 Laboratory evaluation

A local pathologist will evaluate initial and follow-up cervical biopsy specimens. Enrollment diagnosis will be based on the local pathology. These slides will also be reviewed by an expert gynecological pathologist for quality assurance. At the one year follow-up visit, women will have colposcopic-directed biopsies. This pathology will be read by both a local and an expert gynecologic pathologist. The primary endpoint of the study will be the consensus achieved by the local and expert pathologists on the follow-up biopsy samples taken from the colposcopic-directed biopsies at the one year follow up visit. Discrepant cases will be discussed between the two pathologists and if agreement cannot be reached, the case will be reviewed by a third expert pathologist. Consensus will be defined as two of the three pathologists agreeing on the diagnosis. We hope that by using this consensus method, the true incident of CIN2+ will be able to be evaluated and bias in favor of superior cure rates will be avoided. Standard cytology will be taken as per local guidelines. Cytology will be read by a local pathologist and interpreted according to the Bethesda System for classification. ¹⁹ Evaluation of the HPV genotyping will be conducted at the National Cancer Institute.

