The single or double freeze modalities were chosen given the results of the UH2 trial where single-freeze CryoPen® achieved a greater depth of necrosis than double freeze, and the WHO cryotherapy guidelines which endorse CO₂ double-freeze as the standard cryotherapy treatment. While these are the preferred modalities, in a few cases clinicians may decide to repeat the CryoPen® modality to correct placement of the first application and maximize treatment efficacy and patient safety.

We will approach approximately 1,602 women with CIN2+ during a 2.5 year enrollment phase (30 months). Assuming an approximately 80% participation rate, ¹⁰ approximately 1,281 women will be enrolled—1,152 (90%) will be eligible for cryotherapy (i.e. no contraindications) and 129 will be ineligible and undergo alternative treatments. We estimate that approximately 20% will be lost to follow-up at the twelve-month visit, so that we will have complete data on a total of 922 women (57.5% of 1,602) treated with either CO₂-based cryotherapy, LMIC-adapted CryoPen®, or thermoablation. We will monitor the percentages of ineligibles, contraindications, and loss to follow-up in real time and adjust recruitment accordingly to achieve the target sample size. In addition, we will conduct a non-essential 6-week follow-up visit to evaluate adverse effects from the ablative procedures. The primary endpoint of the study will be to determine residual disease at a 12-month follow up visit as determined by colposcopy and four-quadrant biopsies.

Enrollment and Treatment

Enrollment diagnosis will be based on the local pathology. These slides will be read by an expert gynecologic pathologist for quality assurance. At the pre-treatment visit, consented women will be administered a short questionnaire to collect demographic

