One year post-treatment, women will return for a follow-up visit to determine residual disease, which is the primary endpoint. Residual disease will be determined by colposcopy and four-quadrant biopsies. In addition, VIA, cytology, and high-risk HPV DNA testing with careHPV will be performed. Genotyping and next-generation sequencing will be repeated to differentiate between persistent and new infections. The goal is to evaluate which test has the highest sensitivity after an ablative treatment: VIA, cytology, or HPV.

We will use local health systems, including healthcare promoters, to encourage women to return for the follow-up visit. Attempts to contact women who do not return for this visit will continue until 18 months post-treatment. If a woman does not return within this time period, she will be considered lost to follow-up.

At the 12-month visit, the following procedures will be performed:

- 1. Pelvic examination
- 2. Urine pregnancy test
- 3. Unaided VIA
- 4. Cytology
- 5. High-risk HPV testing with careHPV
- 6. Colposcopic evaluation and impression
- 7. Four-quadrant microbiopsy protocol using the protocol for sensitive detection of any recurrent/untreated CIN2+.¹¹ All visible lesions in each quadrant of the cervix (12-3, 3-6, 6-9, and 9-12 o'clock) will be biopsied. Endocervical curettage (ECC) will be performed on all patients. If no lesion is visible in a given quadrant, the most suspicious appearing area in that quadrant will be biopsied.
- 8. Cervical swab collection for HPV genotyping using next-generation sequencing (NGS)

Treatment acceptability questions will again be administered at the end of this visit. Women diagnosed with recurrent/untreated CIN2+ on biopsy will be asked to return to undergo LEEP. Women with suspected cancer on biopsy will be referred to the local cancer hospital for standard of care.

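### The primary endpoint names different 12-month specimens in sections 3.1 and 5.3, and neither says whether CIN2+ found only on endocervical curettage is a treatment failure

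*Combined protocol and SAP*

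**What the plan says.** Section 3.1 (Study design) states the primary endpoint twice. The design text sets out to "determine residual disease at a 12-month follow up visit as determined by colposcopy and four-quadrant biopsies". The 12-month follow-up text repeats it: "Residual disease will be determined by colposcopy and four-quadrant biopsies".

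Item 7 of the 12-month procedure list in section 3.1 describes the sampling, "using the protocol for sensitive detection of any recurrent/untreated CIN2"+. Visible lesions are biopsied in each quadrant. For the other quadrants, "If no lesion is visible in a given quadrant, the most suspicious appearing area in that quadrant will be biopsied". The same item adds: "Endocervical curettage (ECC) will be performed on all patients".

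Section 5.3 (Laboratory evaluation) describes the visit differently: "At the one year follow-up visit, women will have colposcopic-directed biopsies". It then makes the primary endpoint the consensus of the local and expert pathologists "on the follow-up biopsy samples taken from the colposcopic-directed biopsies at the one year follow up visit", with a third pathologist for unresolved disagreements. It mentions neither the four-quadrant scheme nor the ECC.

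Section 3.2 bases the cure fraction on a CIN2+ diagnosis at the twelve-month visit and does not name the tissue, so it does not settle the matter.

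**The concern.** This is the only primary endpoint, and it decides non-inferiority for two devices. Two people following the plan in good faith could classify the same woman differently. The clearest case is a woman whose only CIN2+ is on the ECC. Section 5.3 as written does not count her as a failure, and the endpoint sentences in section 3.1 do not mention the ECC either. A less clear case is a woman whose only CIN2+ lies in a quadrant with no visible lesion.

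The narrow reading also sits badly with the plan's own reasoning. Section 3.2 justifies a control cure range of 50-80%, lower than the literature suggests, because ascertainment here will be more rigorous than the imperfectly sensitive colposcopy of earlier studies. Section 5.3 itself aims to avoid flattering cure rates. An endpoint confined to lesion-directed tissue would work against both.

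Two things are at stake. If failures are missed at similar rates in all arms, a difference on the absolute scale is diluted while the margin stays fixed. And if the rule stays open, the choice of specimens could be made after results are known, or differently across the seven hospitals.

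**Working it through.** **Step 1. The statements side by side.**

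| Place | Directed biopsy of visible lesions | Biopsy of no-lesion quadrants | ECC |
|---|---|---|---|
| 3.1, endpoint sentences (two) | Counted | Counted (four-quadrant) | Not named |
| 3.1, 12-month procedure list | Taken | Taken | Taken from all |
| 5.3, endpoint sentence | Counted | Unclear | Not named |

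No other section reconciles these. The title of the source cited for the sampling scheme (reference 11) lists directed biopsy, random biopsy and ECC as separate items, so they cannot simply be assumed to be one category.

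**Step 2. The plan's own power figure.** Section 3.2 gives 307 women per arm, a 10-point margin, 50% control cure, alpha 0.05 and at least 80% power. With equal cure in both arms:

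- SE = sqrt(2 × 0.5 × 0.5 / 307) = 0.0404, so 0.10/SE = 2.478.
- One-sided 0.05: power = Phi(2.478 - 1.645) = 0.798. This matches the stated figure.
- One-sided 0.025, the level implied by a two-sided 95% CI: power = Phi(2.478 - 1.960) = 0.698.

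The stated power therefore needs one-sided 0.05. The main results below use the two-sided 95% CI, reading section 3.2's intervals as two-sided; step 4 gives the one-sided 5% figures as well.

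**Step 3. Effect of missed failures.** Let m be the share of true failures seen only on uncounted specimens, equal in all arms, with no false positives. Then

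- observed cure = 1 - (1 - m) × true failure rate;
- observed difference = (1 - m) × true difference;
- P(non-inferiority concluded) = Phi((observed difference + 0.10)/SE - 1.96), with unpooled SE and 307 per arm.

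The true difference is set at -10 points, so that concluding non-inferiority is an error. The documents give no value for m, so every value here is an assumption.

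Worked example, control cure 50%, m = 0.20: true failure rates 0.50 and 0.60 become 0.40 and 0.48. Observed cure is 0.60 and 0.52, a difference of -0.08. SE = sqrt(0.60 × 0.40/307 + 0.52 × 0.48/307) = 0.0399. Phi(0.02/0.0399 - 1.96) = 0.072.

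| m (assumed) | Observed difference | False non-inferiority, control cure 50% | 70% | 80% |
|---|---|---|---|---|
| 0 | -10.0 | 2.5% | 2.5% | 2.5% |
| 5% | -9.5 | 3.3% | 3.4% | 3.5% |
| 10% | -9.0 | 4.4% | 4.5% | 4.8% |
| 20% | -8.0 | 7.2% | 8.0% | 9.1% |

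**Step 4. Same check at one-sided 5%.** Replacing 1.96 by 1.645, the error rises from 5.0% to 8.1-8.9% (m = 10%) and 12.6-15.3% (m = 20%) across control cure 50-80%.

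**Step 5. Dropping equal capture.** Take control cure 50%.

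- Capture 75% in control and 80% in the experimental arm: a true -10 becomes (1 - 0.80 × 0.60) - (1 - 0.75 × 0.50) = 0.520 - 0.625 = -10.5 points, against the device.
- Capture 80% in control and 75% in the experimental arm: a true -10 becomes 0.550 - 0.600 = -5 points, in its favour.
- Capture 70% in control and 90% in the experimental arm: truly equal arms show 0.550 - 0.650 = -10 points.

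The direction of bias is therefore not fixed.

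**The case against.** The strongest reply is that section 5.3 is shorthand. Where no lesion is visible, the biopsy is not taken blindly: it goes to the most suspicious area of the quadrant, directly after the colposcopic evaluation in the procedure list. Such a biopsy can fairly be called colposcopic-directed, and the protocol never calls its quadrant biopsies random. Section 5.3 names no tissue to be left unread. The flow diagram and sections 3.1, 3.2 and 9.0 all treat four-quadrant biopsy as the 12-month assessment. On the narrow reading a woman could be sent for further treatment of recurrent CIN2+ and still be recorded as cured, which nobody can have intended. Section 5.3 is also a laboratory section, and section 3.1 contains its own statement of the primary endpoint.

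Most of this stands. A reader might infer that section 5.3 definitely counts disease in a no-lesion quadrant as a cure, or that it is the sole formal definition; the documents support neither. They permit that exclusion but do not require it.

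The reply does not dispose of the ECC. A curettage is not naturally a colposcopic-directed biopsy. It is listed within the four-quadrant item, but no endpoint sentence says that its result counts. If ECC-only disease were the only real gap, the missed share might be small, and at 5% the error rate would move only to about 3.3-3.5%.

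**Conclusion.** The concern holds as an unreconciled definition of the primary endpoint, clearest for the ECC. It is a conflicting rule for the sole primary decision, so it should be settled before the data are analysed.

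Its size cannot be obtained from the documents. With assumed missed shares of 5-20%, equal across arms, false non-inferiority at a true -10 points would be about 3.3% to 9.1% instead of 2.5%. These figures illustrate sensitivity and do not estimate actual bias.

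A reader might also infer that the wording necessarily biases towards non-inferiority. That holds only if capture is similar across arms and false positives are negligible. The devices freeze or heat tissue, and the documents give no evidence that residual disease is equally visible after each; unequal capture could push the result either way.

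**What to change.** Use one endpoint sentence, word for word, in sections 3.1, 3.2 and 5.3. For example: treatment failure is CIN2+ as the worst consensus diagnosis per woman on any protocol-specified 12-month specimen, namely all quadrant biopsies (with or without a visible lesion) and the ECC.

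Then:

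- replace the colposcopic-directed wording in section 5.3 to match;
- state that all these specimens go to consensus reading;
- pre-specify a sensitivity analysis that does not count ECC-only disease as failure.

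Counting the ECC is a choice the sponsor must make explicitly, because the present text does not make it. The sensitivity analysis shows how far the conclusion depends on it.

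The cost is a wording amendment and a little more consensus reading. The tissue is already taken at the visit, so no procedure is added. Observed cure rates may be slightly lower, a case the sample size allows for by taking 50% control cure as its worst case.

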6.0 Recruitment

Hospital clinicians at Salvadorian Social Security Hospital (ISSS) in San Salvador, El Salvador, Hospital Universitario San Ignacio (HUSI), Ginesalud SAS in Bogota, Colombia and the four hospitals in China (Shanxi Bethune Hospital – Shanxi Academy of Medical Sciences (SBH), Yanjin County Women and Children Hospital, Fengqiu County Women and Children Hospital, and Weihui Municipal Hospital for Women and Children Healthcare) will be informed of study criteria and will alert local study coordinators when participants with CIN2+ are scheduled for procedures.

- Our collaborators will be paid per patient during the course of this study. To help ensure that all of the data is obtained, the remainder of the compensation will be provided after the follow-up visit is completed.
- Potential participants will be invited by hospital staff to a private room to learn about the study. This conversation is anticipated to last approximately 30 minutes. The potential participant's family members will be invited to join this conversation if the woman so chooses.
- The study coordinator will assess inclusion/exclusion criteria to confirm eligibility based on the potential participant's clinical record of the most recent pelvic exam, performed either prior to or after her hospitalization, and invite her to participate.
- Participants will be informed that only information necessary to confirm eligibility will be entered into the study data collection form. This form will have a number code for the patient, not the participant's name.
- As part of the information provided, women in El Salvador and Colombia will be informed that their tissue sample will be analyzed in a laboratory in the United States. All women in the study will be informed that results of their analysis and their deidentified information may be published in a peer-reviewed medical journal. Women will be informed that no personal information will be in any analysis of results or publication.

- As part of the information provided, women will be informed that photographs may be taken of the uterine cervix during their procedures. The photographs will be assigned a study number and will not identify the participant. Women may opt out of having photographs taken. De-identified images will be made available to Mobile ODT to develop an algorithm to screen pre-cancerous lesions.
- Women will have the opportunity to ask the study coordinator questions about the study of the study coordinator. In addition, the study coordinator will ask the potential subject to repeat the major points of the study in order to ensure that the woman understands to what she is agreeing and what is expected of her.
- Women who decline to participate will be offered the standard of care treatment for CIN2+.
- The study coordinator will not be the primary doctor for the potential study participants and will not be in a relationship of authority over participants. The study coordinator will explain that the woman's decision to participate in the study will not influence her care.

